10.8. Appendix 8: Alternative Measures During Public Emergencies

The alternative study measures described in this section are to be followed during public emergencies, including the COVID-19 pandemic. This appendix applies for the duration of the COVID-19 pandemic and will become effective for other public emergencies only upon written notification from Pfizer.

Use of these alternative study measures are expected to cease upon the return of business as usual circumstances (including the lifting of any quarantines and travel bans/advisories).

10.8.1. Eligibility

While SARS-CoV-2 testing is not mandated for this study, local clinical practice standards for testing should be followed. A participant should be excluded if they have a positive test result for SARS-CoV-2 infection, is known to have asymptomatic infection, or are suspected of having SARS-CoV-2. Participants with active infections are excluded from the study. When the infection resolves, the participant may be considered for re-screening.

10.8.2. Telehealth Visits

In the event that in-clinic study visits cannot be conducted, every effort should be made to follow up on the safety of study participants at scheduled visits per the [SoA](#) or unscheduled visits. Telehealth visits may be used to continue to assess participant safety and collect data points. Telehealth includes the exchange of healthcare information and services via telecommunication technologies (eg, audio, video, video-conferencing software) remotely, allowing the participant and the investigator to communicate on aspects of clinical care, including medical advice, reminders, education, and safety monitoring.

The following assessments must be performed during a telehealth visit:

- Review and record study intervention(s), including compliance and missed doses.
- Review and record any AEs and SAEs since the last contact.
- Review and record any new concomitant medications or changes in concomitant medications since the last contact.
- Review and record contraceptive method and results of pregnancy test. Confirm that the participant is adhering to the contraception method(s) required in the protocol. Refer to [Section 10.4](#).

Study participants must be reminded to promptly notify site staff about any change in their health status.

10.8.2.1. Laboratory Testing

If a study participant is unable to visit the site for protocol-specified safety laboratory evaluations, testing may be conducted at a local laboratory if permitted by local regulations. The local laboratory may be a standalone institution or within a hospital. The following safety laboratory evaluations may be performed at a local laboratory as indicated in [Section 10.2](#). If a local laboratory is used, qualified study site personnel must order, receive, and review results. Site staff must collect the local laboratory reference ranges and certifications/accreditations for filing at the site. Laboratory test results are to be provided to the site staff as soon as possible. The local laboratory reports should be filed in the participant's source documents/medical records. Relevant data from the local laboratory report should be recorded on the CRF.

If a participant requiring pregnancy testing cannot visit a local laboratory for pregnancy testing, a home urine pregnancy testing kit with a sensitivity of at least 25 IU/mL may be used by the participant to perform the test at home, if compliant with local regulatory requirements. The pregnancy test outcome should be documented in the participant's source documents/medical records and relevant data recorded on the CRF. Confirm that the participant is adhering to the contraception method(s) required in the protocol.

10.8.2.2. Electrocardiograms

If the participant is unable to visit the study site for ECGs, the participant may visit an alternative facility to have the ECGs performed. Qualified study site personnel must order, receive, and review results.

10.8.3. Adverse Events and Serious Adverse Events

If a participant has COVID-19 during the study, this should be reported as an AE or SAE and appropriate medical intervention provided. It is recommended that the investigator discuss temporary or permanent discontinuation of study intervention with the Sponsor before continuing treatment.

10.9. Appendix 9: Grading System for Pro-Inflammatory-Related Adverse Events

Adverse Event	Grade 1	Grade 2	Grade 3	Grade 4	Grade 5
Vomiting	1 - 2 episodes (separated by 5 minutes) in 24 hrs	3 - 5 episodes (separated by 5 minutes) in 24 hrs	≥6 episodes (separated by 5 minutes) in 24 hrs; tube feeding, TPN or hospitalization indicated	Life-threatening consequences; urgent intervention indicated	Death
Diarrhea	Increase of <4 stools per day over baseline; mild increase in ostomy output compared to baseline	Increase of 4 - 6 stools per day over baseline; moderate increase in ostomy output compared to baseline	Increase of ≥7 stools per day over baseline; incontinence; hospitalization indicated; severe increase in ostomy output compared to baseline; limiting self-care ADL	Life-threatening consequences; urgent intervention indicated	Death

Abbreviations: ADL = activities of daily living; TPN = total parenteral nutrition.

10.10. Appendix 10: CRS Grading System and Management

CRS is a non-antigen-specific cytokine-associated toxicity that occurs as a result of high-level immune activation. Cytokine release with fever and headache have been reported to occur with IVIg infusion and meets current criteria for Grade 1 CRS; it may occur with PF-06755347 administration.¹¹ Based upon the mechanism of action of PF-06755347, CRS, if it occurs, is expected to be manageable through awareness and supportive care.

Early recognition and intervention should be undertaken at the first signs or symptoms of CRS; signs may include pyrexia, shivering/rigors, tachycardia, tachypnea and/or hypotension and symptoms may include headache, nausea, chills, vomiting, and back ache when temporally related to PF-06755347 administration in the absence of alternative etiologies.

Grading by the more recent ASTCT CRS criteria¹² (Table 13) will be captured on the CRS CRF.

Table 13. ASTCT CRS Revised Grading System¹²

CRS parameter:	Fever*	With Hypotension	And/or† Hypoxia
Grade 1	Temp. $\geq 38^{\circ}\text{C}$	None	None
Grade 2	Temp. $\geq 38^{\circ}\text{C}$	Not requiring vasopressors	Requiring low-flow‡ nasal cannula, low-flow‡ facemask or blow-by
Grade 3	Temp. $\geq 38^{\circ}\text{C}$	Requiring a vasopressor with or without vasopressin	Requiring high-flow‡ nasal cannula, high-flow‡ facemask, nonrebreather mask, or Venturi mask
Grade 4	Temp. $\geq 38^{\circ}\text{C}$	Requiring multiple vasopressors (excluding vasopressin)	Requiring positive pressure (eg, CPAP, BiPAP, intubation and mechanical ventilation)

Organ toxicities associated with CRS should still be graded according to CTCAE v4.03 and do not influence CRS grading.

* Fever is defined as temperature $\geq 38^{\circ}\text{C}$ and not attributable to any other cause. In patients who have CRS then receive antipyretic therapy, fever is no longer required to grade subsequent CRS severity. In this case, CRS grading is driven by hypotension and/or hypoxia.

† CRS grade is determined by the more severe event: hypotension or hypoxia not attributable to any other cause. For example, a patient with temperature of 39.5°C hypotension requiring 1 vasopressor, and hypoxia requiring low-flow nasal cannula is classified as grade 3 CRS.

‡ Low-flow nasal cannula or facemask is defined as oxygen delivered at ≤ 6 L/min. Low flow also includes blow-by oxygen delivery, sometimes used in pediatrics. High-flow nasal cannula or facemask is defined as oxygen delivered at > 6 L/min. This is modified from original ASTCT criteria to differentiate between low-flow and high-flow facemask.

Abbreviations: ASTCT = American Society for Transplantation and Cellular Therapy; BiPAP = bilevel positive airway pressure; CPAP = continuous positive airway pressure; CRS = cytokine release syndrome; CTCAE = Common Terminology Criteria for Adverse Events.

CRS identification and management (adapted from Neelapu et al¹³)

- Monitor vital signs (temperature, blood pressure, pulse and SpO₂) according to SoA and at a minimum, every 1 hour until vital signs have returned to baseline levels. If clinical symptoms suggestive of CRS are reported by the participant outside of the scheduled windows of the SoA, close monitoring of vital signs should be conducted as above.

Fever (body temperature $\geq 38.0^{\circ}\text{C}$)

- Acetaminophen/paracetamol and cooling blanket for the treatment of fever.
- Non-steroidal anti-inflammatory drugs (NSAIDs) such as ibuprofen/naproxen can be used as second treatment option for fever if not contraindicated.
- Assess for infection using blood and urine cultures and nasal swab for COVID-19 as indicated.
- Initiate oral or IV fluids for hydration as tolerated. Increase fluid rate from the existing IV catheter.

Hypotension (Systolic Blood Pressure < 90 mmHg or a decrease of 20% from baseline levels in either systolic or diastolic blood pressure whichever is lower).

- IV fluid 500 ml of normal saline given as rapidly as the existing safety IV cannula can tolerate.
- May give a second 500 ml of normal saline if participant remains hypotensive or participant's symptoms of hypotension do not resolve.

Corticosteroid Use:

- Up to a total of hydrocortisone 200 mg or dexamethasone 10 mg or methylprednisolone 125 mg IV. should be used if IV fluid does not stabilize blood pressure. At the investigator's discretion, this dose may be split in half, with the first half given during the first Normal Saline infusion and the second half given if symptoms and signs do not improve within one hour. If participant remains hypotensive after full dose of corticosteroids and fluid is administered or is otherwise not responding to therapy, or at investigator's discretion, initiate transfer to ICU for consideration of vasopressors or optional anti-IL-6 agents (tocilizumab 8 mg/kg (maximum dose 800 mg) IV or siltuximab 11 mg/kg IV).

Hypoxia

- If SpO₂ $< 94\%$, initiate supplemental oxygen via nasal cannula or low flow mask, and increase flow to maintain SpO₂ to $\geq 94\%$.
- Initiate transfer to ICU at investigator's discretion, or if oxygen flow rate exceeds 6 L/min or mask with fraction of inspired oxygen (FiO₂) $> 40\%$.

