6.6. Dose Progression

The participants within each cohort will be dosed using a sequential dosing scheme. For all cohorts, a single participant will be dosed at a given time, followed by a minimum of 72-hour (for IV) and 96-hours (for SC) safety monitoring period. In total there will be a minimum of 96 hours between each IV participant dosed and 120 hours for each SC participant dosed.

The following rules will be applied when considering dosing of the next participant in the cohort.

Sequential dosing may **proceed** only if no adverse events are reported OR all of the following criteria are met:

1. Any pro-inflammatory events are < Grade 2 Per CTCAE criteria in [Appendix 9](#).
2. All other adverse events are deemed mild or moderate in severity, regardless of relatedness.
3. Any laboratory, ECG or vital sign changes are considered not clinically significant.
4. No other pause or stop criteria are met.
5. For participants with ITP, in addition to the above criteria, no participant has greater than a 30% decrease in platelet count – defined from the immediate pre-dosing platelet count to the lowest postdosing platelet count. Dose progression will be independent of dose progression from HP cohorts at higher dose levels.

Sequential dosing should be **paused** if any criterion below is met in a participant receiving active drug:

1. Grade 2 (Objective) pro-inflammatory event (vomiting, diarrhea, hypotension or hypoxia) (see [Appendix 9](#)).
2. Adverse event which is considered to be severe (Grade 3 or higher) AND is deemed related to study intervention.
3. A moderate event (Grade 2) AND is deemed related to study intervention not otherwise identified as a proinflammatory event or AE of special interest, that in the opinion of the PI and Sponsor are of concern and warrant further investigation before additional dosing.
4. For participants with ITP, platelet count of <30 x 10⁹/L AND a decrease from baseline ≥30%, or a platelet count decrease from baseline of ≥50%, defined from the immediate pre-dosing platelet count to the lowest post-dosing platelet count, or a bleeding or bruising-related AE CTCAE 4.03 Grade 2 or higher (except metrorrhagia Grade 3 or higher).

Sequential dosing should be **stopped** at the current dose level if any criterion below is met in participant receiving active drug:

1. Grade 3 or greater pro-inflammatory event.
2. Serious adverse event that is deemed related to study intervention.

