8.2.2. Vital Signs

Supine BP will be measured with the participants arm supported at the level of the heart, and recorded to the nearest mm Hg after approximately 5 minutes of rest. The same arm (preferably the dominant arm) will be used throughout the study. Blood pressure should be taken from the contralateral arm to that receiving infusion. Participants should be instructed not to speak during measurements.

The same properly sized and calibrated BP cuff will be used to measure BP each time. The use of an automated device for measuring BP and pulse rate is acceptable, however, when done manually, pulse rate will be measured in the brachial/radial artery for at least 30 seconds. When the timing of these measurements coincides with a blood collection, BP and pulse rate should be obtained prior to the nominal time of the blood collection. Triplicate vital signs measurement (including oral temperature) at the times specified in the [SoA](#) should be collected approximately 2 minutes apart.

Additional collection times, or changes to collection times, of BP and pulse rate will be permitted, as necessary, to ensure appropriate collection of safety data.

Normal range for vital sign measurements are defined as: $90 \text{ mmHg} \leq \text{systolic BP} \leq 139 \text{ mmHg}$; $50 \text{ mmHg} \leq \text{diastolic BP} \leq 89 \text{ mmHg}$; $40 \text{ bpm} \leq \text{heart rate} \leq 100 \text{ bpm}$; $35.4^\circ\text{C} \leq \text{oral temperature} \leq 37.5^\circ\text{C}$.

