	
Rationale: to provide predicted exposures for planned SC dose levels.
 
6. Section 5.2 Exclusion Criteria: added language to #17 that an approved COVID-19 vaccine is considered a concomitant medication. Language has been added that participants that have received an approved vaccine should allow 28 days prior to dosing with PF-06755347.
 
Rationale: to provide clarity on vaccine administration during the pandemic.
 
7. Section 6.5.1 Rescue Medication: updated to include language regarding the availability of specific medications and an ICU.
 
Rationale: added per regulatory feedback.
 
8. Section 6.6 Dose Progression: stop criteria was updated.
 
Rationale: The previous protocol amendment stated in Section 6.6 Dose Progression included stopping criteria where the study would be stopped. The clinical findings to date with the IV route illustrate an understanding of the time course of adverse events, CRS and laboratory abnormalities. As a result, the proposal is to restart the study with SC administration because it is anticipated that the severity of CRS is potentially related to C_{max}. Therefore, the SC route is predicted to decrease the C_{max} by about 4-fold; thus reducing the risk to participants and the need to stop the study.
 
9. Section 10.8 Appendix 8 removed hypoxia and hypotension from the Grading System of Pro-Inflammatory-Related Adverse Events table.
 
Rationale: to minimize confusion as these events are part of the CRS grading table in Section 10.9 Appendix 9.
 
10. Section 10.9 Appendix 9: CRS Grading System and Management Guidelines: updated to be

--	--

		
more specific for the management of CRS and use of medication.
 
Rationale: to provide clarification and clearer expectations.
 
11. PACL dated 29 Sept 2020: clarifications were implemented into Section 1.2 Study Schematic to include a footnote referring to Section 4.2 stating that actual dose levels are subject to change.
 
Rationale: to be consistent with language stated in Section 4.2 and 4.3.1.3 regarding dose adjustment.

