Appendix 1. Categorical Classes for ECG and Vital Signs of Potential Clinical Concern

Categories for QTcF

| | | | |
|----------------------------------|------------------|------------------|------------|
| QTcF (ms) | 450 < max. ≤ 480 | 480 < max. ≤ 500 | max. > 500 |
| QTcF (ms) increase from baseline | 30 < max. ≤ 60 | max. > 60 | |

Categories for PR and QRS

| | | |
|---------------------------------|--|--|
| PR (ms) | max. ≥ 300 | |
| PR (ms) increase from baseline | Baseline > 200 and max. ≥ 25% increase | Baseline ≤ 200 and max. ≥ 50% increase |
| QRS (ms) | max. ≥ 140 | |
| QRS (ms) increase from baseline | ≥ 50% increase | |

Categories for Vital Signs

| | | |
|---|--------------------|--------------------|
| Systolic BP (mm Hg) | min. < 90 | |
| Systolic BP (mm Hg) change from baseline | max. decrease ≥ 30 | max. increase ≥ 30 |
| Diastolic BP (mm Hg) | min. < 50 | |
| Diastolic BP (mm Hg) change from baseline | max. decrease ≥ 20 | max. increase ≥ 20 |
| Supine pulse rate (bpm) | min. < 40 | max. > 120 |

Measurements that fulfill these criteria are to be listed in report.

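### Appendix 10's hypotension definition, the only numeric one in the documents, joins its limits with *or* and then adds *whichever is lower*, so the same fall in blood pressure may or may not count

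*Protocol*

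**What the plan says.** **The definition.** In the management part of Protocol Section 10.10 (Appendix 10), the line that introduces the fluid steps defines hypotension as "Systolic Blood Pressure < 90 mmHg or a decrease of 20% from baseline levels in either systolic or diastolic blood pressure whichever is lower".

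**The grading table.** In Table 13 of the same appendix, a participant with fever and neither hypotension nor hypoxia is Grade 1. Hypotension makes it Grade 2 if it is "Not requiring vasopressors". The table gives no mmHg or percentage limit. Its footnotes say that "CRS grade is determined by the more severe event: hypotension or hypoxia not attributable to any other cause". After antipyretic treatment fever is no longer needed: "In this case, CRS grading is driven by hypotension and/or hypoxia".

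**The dosing rule.** Pause criterion 1 in Section 6.6 is a "Grade 2 (Objective) pro-inflammatory event (vomiting, diarrhea, hypotension or hypoxia"), with a pointer to Appendix 9. Appendix 9 grades only vomiting and diarrhea. The amendment history explains the gap: Amendment 5 "removed hypoxia and hypotension from the Grading System of Pro-Inflammatory-Related Adverse Events table", on the ground that the CRS table already covered them.

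**Other blood pressure limits.** Section 8.2.2 ("Normal range for vital sign measurements are defined as") has a systolic lower bound of 90 and a diastolic lower bound of 50 mmHg. SAP Appendix 1 ("Categories for Vital Signs") flags systolic pressure below 90 or a fall of at least 30 mmHg, and diastolic pressure below 50 or a fall of at least 20 mmHg. Neither is called hypotension or linked to CRS grading.

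**The concern.** A list joined by *or* is met when any item is met. A closing *whichever is lower* tells the reader to pick one item. Both instructions cannot operate on the same list, and the sentence does not say which quantities are compared. Two candidates are plausible: the fixed 90 mmHg against the 20% systolic limit, or systolic against diastolic pressure.

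The sentence starts the CRS treatment steps, so the ambiguity already matters there. If it also supplies the missing threshold for Table 13, it decides Grade 1 versus Grade 2 for a participant with no hypoxia and no vasopressor, and that grade is recorded on the CRS CRF. Hypotension is also named in pause criterion 1, and the appendix that criterion cites cannot resolve it. Two investigators who see the same readings could reach different answers in good faith.

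**Working it through.** The plan states no figure to reproduce. The check applies each reading to the same blood pressures.

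**Inputs.** The limits come from Appendix 10: systolic pressure (SBP) below 90 mmHg, and a 20% fall in SBP or diastolic pressure (DBP). Baselines run up to 139 mmHg systolic, because screening SBP of 140 or more is excluded (Sections 5.2 and 5.4) and the Section 8.2.2 normal range is 90-139. A 20% fall is taken as a value at or below 0.8 × baseline.

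**Readings.**
- A, any limb suffices: SBP < 90, or SBP ≤ 0.8 × baseline, or DBP ≤ 0.8 × baseline.
- B1, the lower systolic limit governs and the diastolic limb stays as a separate trigger: both SBP < 90 and SBP ≤ 0.8 × baseline, or else DBP ≤ 0.8 × baseline.
- B2, as B1 with the diastolic limb dropped.
- C, *lower* refers only to the systolic/diastolic pair: SBP < 90 stands alone, plus a 20% fall in the *lower* of the two pressures.

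**Where the systolic limits meet.** 0.8 × baseline = 90 gives baseline = 90 / 0.8 = 112.5 mmHg. Elsewhere:

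| Baseline SBP | 0.8 × baseline | Limit under A | Limit under B1/B2 | SBP values where they differ |
|---|---|---|---|---|
| 100 | 80 | 90 | 80 | 81-89 |
| 120 | 96 | 96 | 90 | 90-96 |
| 130 | 104 | 104 | 90 | 90-104 |
| 139 | 111.2 | 111.2 | 90 | 90-111 |

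Below 112.5 the fixed 90 mmHg limb has no effect under B1 or B2; above it the 20% systolic limb has none. At baseline 100, an SBP of 81-89 would not be hypotension on the systolic limits, although it meets the sentence's own first limb and lies below the Section 8.2.2 lower bound.

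**Worked records.**

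| Baseline to observed | SBP fall | DBP fall | A | B1 | B2 | C |
|---|---|---|---|---|---|---|
| 120/75 to 94/64 | 21.7% | 14.7% | yes | no | no | depends |
| 100/70 to 85/60 | 15.0% | 14.3% | yes | no | no | yes |
| 125/75 to 108/58 | 13.6% | 22.7% | yes | yes | no | yes |
| 120/75 to 88/62 | 26.7% | 17.3% | yes | yes | yes | yes |

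The first record depends, under C, on what *lower* means within the pair. It counts if the pressure with the greater fall is meant (systolic, 21.7%). It does not count if the numerically lower pressure is meant (diastolic, 14.7%). With fever, no hypoxia and no vasopressor, *yes* gives Grade 2 and *no* gives Grade 1, if this sentence is used for grading.

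**Illustrative frequency.** The documents give no blood pressure distribution, so these inputs are assumptions: baseline mean SBP 115, 120 or 125 (SD 10, limited to 90-139) with mean DBP 70, 72 or 76 respectively (SD 8, limited to 50-89); falls averaging 18% (SD 6% systolic, 8% diastolic); 400,000 draws per setting. A and B1 disagree in 15-17% of participants; A and B2 in 46-52%. The mean fall sits just under the 20% limit, which pushes disagreement up.

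**The case against.** **It is a treatment heading, not a grading rule.** Table 13 does not cite the sentence, and pause criterion 1 points to Appendix 9. This stands: the grading role is an inference from its being the only numeric definition, in an appendix that covers both grading and management. If it is not meant for grading, Table 13 has no hypotension threshold at all.

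**A sensible reading removes much of the problem.** *Whichever is lower* directly follows the systolic/diastolic pair and may attach only to it. SBP below 90 then stands alone, and the apparent clash with Section 8.2.2 disappears. If the greater fall within the pair is meant, the result equals the any-limb reading. This is fair, and it is why the wording is ambiguous rather than contradictory. The text does not select that reading, however, and if it is intended the phrase adds nothing.

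**Other safeguards apply.** Section 6.6 lets dosing proceed after adverse events only if vital sign changes are judged not clinically significant. Each participant's 72- or 96-hour data are reviewed before the next is dosed, and pause criterion 3 covers related moderate events of concern. These reduce the chance that an important fall passes unnoticed. They do not settle the grade.

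**Hypoxia also separates Grade 1 from Grade 2.** Correct, so the ambiguity changes the grade only when there is no hypoxia and no vasopressor.

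**Conclusion.** The concern holds as an ambiguity in a safety threshold. Neither document says what *whichever is lower* compares, and the answer changes whether ordinary readings count as hypotension: by 10 mmHg in the systolic limit at baseline 100 (90 against 80) and by 14 mmHg at baseline 130 (104 against 90). That arithmetic needs no distributional assumption. The 15-17% and 46-52% figures do, and the larger one also requires dropping a diastolic limb that the sentence expressly includes; neither estimates what happened in the trial.

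Two stronger inferences are not supported. A reader might conclude that the ambiguity undermines the IV maximum tolerated dose. Section 2.1 places both Grade 1 and Grade 2 CRS at doses above the 0.3 mg/kg maximum and does not say that the split between those grades set it; nor do the documents show that this sentence governed the IV grades. A reader might also conclude that CRS grades cannot be compared across cohorts. That goes too far: the grading role is inferred, only cases without hypoxia or vasopressor use are affected, and CRS grade is not a named endpoint in the legible text of Section 3.

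**What to change.** - Reconcile the Appendix 10 sentence so that any pair of baseline and observed readings gives one result. State whether any limb is sufficient, and explain or remove *whichever is lower*.
- Check the reconciled wording against its own 90 mmHg limb and the Section 8.2.2 normal range.
- Cite that single definition from Table 13 and from pause criterion 1, whose present pointer leads to a table with no hypotension row.
- Optionally, list recorded baseline and event SBP and DBP beside the investigator-assigned CRS grade, for review. Do not regrade by program: Table 13 requires that hypotension have no other cause, which pressure values alone cannot establish.

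Which threshold applies is for the sponsor and investigators to decide. The cost is one sentence and two cross-references in the next amendment, plus one optional listing from vital signs already collected.
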